MAINTAINING IMPLEMENTATION
THROUGH DYNAMIC ADAPTATIONS

MIDAS Quality Enhancement Research Initiative

Center for Clinical Management Research

[name]

[name]

[contact]

Official Title of Project: MIDAS Cluster Randomized Controlled Trial of Implementation Strategies to Optimize Use of Medications in VA Clinical Settings (MIDAS cRCT)

ClinicalTrials.gov ID: NCT05065502

Date: 09/24/2025

Please find the Study Protocol and Statistical Analysis Plan below. Since the creation of this document, the following changes have been made to the analysis plan:

- Data was collected through 18 months post-baseline rather than through 36 months due to time constraints.
- Instead of a patient-level dichotomous response over time, the differences between arms were modelled as a single outcome adjusting for the evidence-based practice (EBP) and the level of potentially inappropriate medications (PIMs) in the pre-period to address the large difference in PIMs between EBPs.
- After conducting additional testing of our algorithm for detecting CBTI sessions, we found the algorithm to be adequately sensitive to detecting *any* CBTI but not accurate for detecting the number of CBTI sessions (e.g., CBTI could often be mentioned in the context of a referral or some other ongoing treatment). Thus, the secondary outcome “Change in Mean Cognitive Behavioral Therapy for Insomnia (CBTI) Sessions Completed” could not be analyzed.
- We had originally planned for all CBTI sites to provide information regarding where in the medical records we could identify referrals. However, prior to launching the trial, we determined several of the sites' processes for referrals were not distinguishable as referrals vs. other forms of communication (e.g., adding a therapist as a cosigner to a note), making collection of this data impractical. Thus, we did not have sites collect referral criteria and the secondary outcome “Change in the Monthly Percentage of Patients Referred to Cognitive Behavioral Therapy for Insomnia (CBTI) Across Facilities” could not be analyzed.

A protocol paper for this project, titled “Maintaining Implementation through Dynamic Adaptations (MIDAS): protocol for a cluster-randomized trial of implementation strategies to optimize and sustain use of evidence-based practices in Veteran Health Administration (VHA) patients,” was published in May 2022.

[name], MS
Principal Investigator

Aims

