Mixed methods analyses will be used to evaluate the following three aims:

1. *To compare the effectiveness of two implementation strategies (LEAP Quality Improvement Learning Program + Academic Detailing (AD) vs. AD alone) on potentially inappropriate medication use, using a pooled analysis of effects across three trials at 18 months, two years, and three years post-baseline at the clinic-level, based on monthly assessed data from 13-36 months;*
2. *To compare the effectiveness of the two implementation strategies on secondary outcomes specific to each trial at 18 months, two years, and three years post-baseline, based on monthly assessed data from 13 to 36 months; and*
3. *To explore the effects of implementation, provider behaviors and experiences, and context, on sustained improvements in potentially inappropriate medication use.*

Methods

Clinic Randomization

Within each trial, clinics will be randomized after assenting to participate (equivalent to enrollment). Clinics will be assigned to one of two arms by a statistician, stratified further by clinic type (medical center, community clinic, or Community Living Center) if needed to ensure partial balance between arms with respect to potential confounders associated with culture and complexities associated with clinic location [1,2].

Outcomes and Analyses

As part of a pooled analysis, we will compare the same two implementation strategies across all three EBPs and take a unified approach to implementation and evaluation across the trials. Table 1 shows MIDAS measures, data collection timeframe, and data sources. While a unified dichotomous outcome, i.e., potentially inappropriate medications, was identified for each trial to allow for the pooled analysis, each trial will also be analyzed individually (see Table 1).

Table 1: MIDAS Measures showing Data Sources and Timepoints by Aim

Aim	Type	Source
Aim 1: Primary outcome		
Service Outcomes		
Proportion of potentially inappropriate care	Quantitative	CDW administrative data
Aim 2: Secondary outcomes		
Service Outcomes		
VIONE Trial		
Potentially inappropriate use of proton pump inhibitors (PPIs), aspirin, and CNS active medications (e.g., muscle relaxants), analyzed one at a time	Quantitative	CDW administrative data
Monthly medication costs for all drugs	Quantitative	CDW administrative data
Number of pharmacist medication reviews	Quantitative	CDW administrative data

Aim	Type	Source
DOAC Trial		

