For *first-line treatment for insomnia*, the outcome will be the proportion of patients with a new prescription for a sedative-hypnotic medication who have not had CBTI in the prior 12 months out of all primary care patients actively following with the clinic and are not in hospice/palliative care.

For all three trials, medication use (yes/no) and possession of active prescription for each month will be determined using exposure days based on supply days, and use will be determined by the exposure status on day 1 of each month. We will also do sensitivity analyses based on the criteria of use anytime during the month as well as PIMs defined to medications used chronically, for example, greater than 90 of the 180 prior days.

For each trial we will first compare demographic characteristics (age, sex, and race) of patients at risk of potentially inappropriate medications in the first month of implementation between the two arms. We will then obtain, for each trial by arm, crude monthly percentages (along with the corresponding 95% confidence intervals) of potentially inappropriate medications, averaged across clinics randomized to each arm and weighted by clinic-month size. For each trial, we will plot the monthly clinic level percentages over the follow-up 13-36 months to graphically assess if the difference between the two arms can be meaningfully summarized across the three trials with the unified outcome. If we find, for example, that trends between-arms over post-implementation months differ notably across the three trials, unified results comparing AD+LEAP vs. AD arm across trials may not be meaningful, and we will only conduct analyses separately by each trial.

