For comparison between arms, we will use generalized estimating equations (GEE) with clinic level monthly percent of potentially inappropriate medications among patients at risk during post implementation period (months 13 to 36) as the dependent variable. The model will include indicators of two trials with one trial as the referent category to account for differing underlying levels of inappropriate medication use across trials. The model will also include follow-up time in months and the LEAP+AD arm indicator with AD as the referent category and will adjust for serial correlation within clinic over time. We will also include time by arm interaction to assess if the magnitude of the difference between LEAP+AD vs. AD changes over time. If the interaction is significant, we will estimate between-arm difference at 18 months as well as at 2- and 3-years separately based on the model with the interaction term. On the other hand, if the interaction is not significant, this would indicate between-arm difference not to differ at the three follow-up times of interest (18, 24, and 36 months), and thus we will drop the interaction term and the parameter estimate of the LEAP+AD arm indicator will be used to estimate the time-averaged difference in percentage of patients with inappropriate medications during post-implementation period in clinics randomized to LEAP+AD compared to clinics randomized to AD.

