If we find notable baseline demographic difference between arms within trials, we will use a generalized linear mixed model (GLMM) with logit link to estimate the between-arm difference while adjusting for baseline age, sex, and race difference with monthly person level response (yes/no) data from post-implementation period of months 13 to 36. In addition to time, AD+LEAP indicator and trial type indicators as predictors, the GLMM model using patient level data will include patient age, sex, race, and random intercepts for patients nested within clinic to adjust for potential correlation within clinics and serial correlation over time. The parameter estimate for the LEAP+AD arm indicator will be used to estimate the time-averaged odds of inappropriate medication use during the post-implementation period for patients in clinics randomized to LEAP+AD compared to the odds of the same patients if their clinics were randomized to AD. Although the GEE and GLMM models give different summary estimates with different interpretations, the GLMM model allows for adjusting for patient characteristics, and a consistent substantive conclusion will assure us of the evidence for the effect of LEAP when added to AD. Similar to the GEE model, we will test if the odds ratio of LEAP+AD vs. AD changes over time by including time by arm interaction term, and if the interaction term is significant, we will obtain adjusted ORs associated with LEAP+AD compared to AD at 18 months, 2-years, and 3-years.

For each trial we will also compare AD and AD+LEAP to usual care controls. To do this, we will perform a non-randomized secondary analysis for each trial. The analysis will have the same primary outcome variable and use the same generalized linear mixed model (GLMM) with logit link. The primary control group will be all non-participating sites. We will also use a secondary analysis, where for each intervention site we will have two control sites that are matched on clinic size (within 50%), pre-intervention outcome rate (within 30 rankings of all sites), and region of the country. These analyses will adjust for the clinic-level variables clinic size, intervention outcome rate, region of the country and the patient-level variables age, sex, and race.

Aim 2: Secondary Outcomes and Analyses

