Secondary outcomes for VIONE will be the prevalence of potentially inappropriate use of PPIs; the prevalence of potentially inappropriate use of aspirin; and the prevalence of potentially inappropriate use of CNS active medications (muscle relaxants, anti-psychotics, Z-drugs, and

benzodiazepines) or anticholinergic drugs; number of inappropriate medications at a patient level; monthly medication costs for all drugs, without regard to appropriateness; and number of pharmacist medication reviews.

Secondary outcomes for the DOAC trial will be the sub-components of the “flags” on the dashboard. These include potential mis-dosing, potential medication interactions, or concern for nonadherence. This follows the organizational structure of both the presentation of the flags on the dashboard and the key messages provided to the academic detailing and LEAP teams. Process outcomes will be how often the provider uses the dashboard and rates of new DOAC starts compared to warfarin starts. These outcomes will be kept in alignment with our other work using the dashboard [4].

In stand-alone analyses of the CBTI trial, the primary outcome will be the prevalence of any CBTI receipt among primary care patients actively following with the clinic who are not in hospice/palliative care.

Analyses of secondary outcomes such as percent of potentially inappropriate use of PPI or mean number of CBTI sessions at each clinic month will be similar to that of the primary outcome using the GEE model accounting for correlation over time. We will also conduct separate analyses by trial with the dependent variables that are unique to each trial. For example, for the polypharmacy trial, secondary outcome of interest is count of medications flagged as inappropriate based on Beers’ criteria [3]. We will compare monthly rates of Beers’ list medication use between implementation strategies using generalized linear mixed models with log link.

Aim 3: Exploration of Potential Predictors of Clinical Outcomes

Our process evaluation will follow a multi-phase concurrent nested mixed methods design [5]. This design has three purposes: 1) help prepare all stakeholders and participants prior to the start of each trial; 2) monitor progress of implementation; and 3) explain summative findings. Overall priority is placed on quantitative methods that guide the trials, while qualitative methods are embedded or “nested” within conduct of the trials.

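### A non-significant time-by-arm test is read as showing equal effects at 18, 24 and 36 months, and the time-specific effects are estimated only if that test is significant

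*Combined protocol and SAP*

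**What the plan says.** The Aims section sets the primary comparison "using a pooled analysis of effects across three trials at 18 months, two years, and three years post-baseline at the clinic-level". Aim 2 asks for the same three times: "on secondary outcomes specific to each trial at 18 months, two years, and three years post-baseline". Neither statement carries a condition.

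The GEE paragraph under Aim 1 sets a two-branch rule. If the time-by-arm interaction is significant, differences at 18, 24 and 36 months are estimated from the model with the interaction. Otherwise, "if the interaction is not significant, this would indicate between-arm difference not to differ at the three follow-up times of interest"; the term is dropped and the arm coefficient is reported as a time-averaged difference. The GLMM paragraph uses the same trigger: "if the interaction term is significant, we will obtain adjusted ORs associated with LEAP+AD compared to AD at 18 months, 2-years, and 3-years". No significance level, equivalence margin or power is given for the interaction test.

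Two other passages under the Aims bear on this. Before modelling, the plan reports, by trial and arm, "crude monthly percentages (along with the corresponding 95% confidence intervals) of potentially inappropriate medications". Under Aim 2, the secondary analyses "will be similar to that of the primary outcome using the GEE model accounting for correlation over time", with no mention of an interaction test.

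The cover note lists later changes. One is "Data was collected through 18 months post-baseline rather than through 36 months due to time constraints". Another is that "the differences between arms were modelled as a single outcome adjusting for the evidence-based practice (EBP) and the level of potentially inappropriate medications (PIMs"; the level adjusted for is the pre-period one. It does not say what happened to the interaction test, and this change does not mention the secondary outcomes.

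**The concern.** There are two faults. The first is logical: a test that fails to reject equal effects over time is treated as evidence that they are equal. That would need an equivalence margin, or at least an interval for the change in effect narrow enough to exclude changes that matter. The second is a mismatch with the aims: whether the promised time-specific estimates are produced depends on the result of a test.

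Fading is part of the trial's question, since Aim 3 concerns sustained improvement. Where the rule is applied, a possibly weak test could support a claim that the effect was held. The month-18 difference, the only named time still observable, would then not be reported with its own interval.

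**Working it through.** **No figure to reproduce.** The documents give no number of clinics, alpha, power, effect size, ICC or autocorrelation. The first step is a comparison of text. The other two are illustrations under stated assumptions: two-sided alpha 0.05, time as one linear term, generalized least squares and every month observed.

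**1. Text against text.** Aim 1 names three times without condition. The GEE paragraph estimates effects at those times in one branch and removes the term needed to estimate them in the other. The GLMM paragraph gives time-specific odds ratios in the significant branch and offers no alternative. The conclusion that the rule is wrong needs no numbers.

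**2. Planned window, months 13-36.** Let D be the effect at month 18, set so that a constant effect D has 80% power in the averaged model. The mean month is 24.5. If the effect halves from month 18 to 36, the average is 1 - 0.5 × (24.5 - 18)/18 = 0.82 D. If it disappears by month 36, the average is 1 - 6.5/18 = 0.64 D. Power of the interaction test:

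| Assumed within-clinic correlation | Effect halves | Effect disappears |
|---|---|---|
| AR(1) 0.5 | 9% | 22% |
| AR(1) 0.8 | 11% | 30% |
| AR(1) 0.95 | 23% | 68% |
| Clinic share 0.5 + AR(1) 0.8 | 33% | 86% |
| Clinic share 0.8 + AR(1) 0.8 | 79% | about 100% |
| Clinic share 0.8 + independent months | about 100% | about 100% |

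In the first four rows, when the test is not significant and the averaged 95% interval stands in for the month-36 effect, it covers the true value about 85-86% of the time (halving) or 56-57% (disappearing). So the test may be weak or strong, depending on a correlation the documents do not give.

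**3. Observed window, assumed to be months 13-18.** The model is a clinic intercept (variance share ICC: 0.2, 0.5, 0.8, 0.95) plus AR(1) error (share 1 - ICC; rho 0, 0.5, 0.8, 0.9). In this balanced layout, the estimated mean and centred slope of the arm difference are uncorrelated. The number of clinics cancels from every ratio below.

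- *Offset.* The mean of months 13 to 18 is 15.5. If the difference changes by b per month, the average is off by (18 - 15.5)b = 2.5b at month 18.
- *Slope precision.* For rho 0, the sum of squares of n consecutive months is n(n² - 1)/12: 24 × 575/12 = 1150 for months 13-36 and 6 × 35/12 = 17.5 for months 13-18. The slope standard error (SE) is larger in the short window by √(1150/17.5) = 8.11. For rho 0.5, 0.8 and 0.9 the ratios are 6.04, 3.99 and 3.11. ICC does not affect them.
- *Power.* A slope with 80% power over months 13-36 lies 1.96 + 0.84 = 2.80 SE from zero. In the short window this becomes 2.80/8.11 = 0.345, so power is P(Z > 1.615) + P(Z < -2.305) = 0.053 + 0.011 = 0.064. For the other rho values power is 0.075, 0.108 and 0.147.
- *Error at month 18.* For that slope, 2.5b is 0.05-0.43 SE of the averaged estimate.
- *Coverage of the month-18 effect under the rule* (averaged interval if |z| for the slope is below 1.96, otherwise the interaction-model interval), by numerical integration. The steep slope has 50% interaction power within months 13-18. It is 1.96 × 8.11/2.80 = 5.7 times the first slope at rho 0, and 1.96 × 3.11/2.80 = 2.2 times at rho 0.9.
- *Cost of keeping the interaction.* Month-18 interval width relative to the averaged interval is √(1 + 2.5² × Var(slope)/Var(mean)). For ICC 0.2 and rho 0, Var(mean) is proportional to 0.2 + 0.8/6 = 0.333 and Var(slope) to 0.8/17.5 = 0.0457, which gives √(1 + 6.25 × 0.0457/0.333) = 1.36.

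| ICC (range over rho) | Coverage, 80%-power slope | Coverage, steep slope | Width ratio |
|---|---|---|---|
| 0.2 | 0.920-0.929 | 0.754-0.905 | 1.094-1.363 |
| 0.5 | 0.935-0.940 | 0.871-0.924 | 1.056-1.158 |
| 0.8 | 0.944-0.947 | 0.926-0.940 | 1.021-1.052 |
| 0.95 | 0.949 | 0.945-0.948 | 1.005-1.012 |

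**The case against.** The strongest reply is that the rule is largely superseded. With data ending at month 18, effects at 24 and 36 months can no longer be compared, and a single modelled outcome appears to leave no time-by-arm term. This stands for the primary comparison, although the note does not expressly withdraw the test or say whether the single outcome is a month-18 value, an average or another contrast. Whether the test applies to the secondary outcomes is also not settled.

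The harm shown is also modest. Low power against a slope that moves the month-18 value by less than half an SE is no surprise. The worst coverage needs low ICC and a slope that nothing in the documents supports. This stands too, and in the planned window low power cannot be asserted as fact.

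The plan also calls its estimate time-averaged, which is a legitimate estimand, and it shows crude monthly percentages with intervals. Fading would therefore be visible. But those percentages are unadjusted and given separately by trial and arm, so they do not supply a modelled between-arm difference with its own interval.

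Finally, the GLMM paragraph gives weaker support than the GEE paragraph. It does not claim that non-significance shows equality, and this between-arm model runs only if baseline demographics differ notably. None of these points rescues the stated inference.

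**Conclusion.** The concern holds, as a minor point about the written rule. Non-significance is taken to show constancy, and estimates that Aim 1 promises outright are made conditional on a test. This conclusion does not depend on the illustrations.

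The size does depend on them. If the rule is still used on months 13-18 with a linear trend, a non-significant result says little about constancy, but the averaged interval is a reasonable stand-in for the month-18 effect unless the slope is steep and the ICC low. The rule matters for any GEE, GLMM or secondary analysis that still uses a time-by-arm test. It probably does not affect the primary comparison as the cover note describes it.

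**What to change.** - Delete the statement that a non-significant interaction shows equal differences at the three times.
- Wherever time-by-arm is modelled, report the 18-month difference (and any later named month actually observed) with its confidence interval from the model that keeps the interaction, whatever the p-value. Do the same for the GLMM odds ratios.
- Keep the time-averaged difference, labelled as an average over the months analysed, and treat the interaction test as descriptive.
- State whether the interaction test survives the cover-note changes, for the primary and for the secondary outcomes.

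This costs SAP wording and one extra reported estimate, with no new data. Assuming months 13-18, the month-18 interval is about 1-16% wider than the averaged one for ICC 0.5-0.95 and 9-36% wider for ICC 0.2. It also relies on the linear trend holding at the edge of the window, so that assumption should be stated beside it.

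### Random intercepts alone do not model serial correlation that fades with lag, so the GLMM's time-by-arm test is anti-conservative wherever such correlation is present

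*Combined protocol and SAP*

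**What the plan says.** The Aim 1 section makes a clinic-level GEE the planned comparison between arms. If baseline demographics differ notably between arms, a logistic GLMM is fitted to "monthly person level response (yes/no) data from post-implementation period of months 13 to 36". Its correlation structure is "random intercepts for patients nested within clinic to adjust for potential correlation within clinics and serial correlation over time". The section names no autoregressive term, random slope, clinic-by-month effect or robust variance for this model.

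The same GLMM is used to check, through a time-by-arm term, whether the arm effect varies by month. The rule attached to that check reads "if the interaction term is significant, we will obtain adjusted ORs associated with LEAP+AD compared to AD at 18 months, 2-years, and 3-years". The test therefore decides whether time-specific odds ratios are reported.

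Three other statements bear on the point:

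- **Exposure (Aim 1).** Medication use "will be determined using exposure days based on supply days", with status taken on the first day of each month.
- **Usual care (Aim 1).** The non-randomized comparison of each strategy with usual care will "use the same generalized linear mixed model (GLMM) with logit link".
- **Cover note.** "Data was collected through 18 months post-baseline rather than through 36 months due to time constraints". The note also says that the arm difference was modelled as one outcome in place of the patient-level yes/no response over time.

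**The concern.** A random intercept makes some patients or clinics consistently higher than others. Given the intercept, the model treats successive months as independent, so on the logit scale months 13 and 14 are as strongly correlated as months 13 and 36.

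The exposure rule makes that unlikely. A fill that covers several months fixes a patient's status on several successive first-of-month dates and says little about dates far off. Clinics may also drift.

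The arm effect averaged over time depends on differences between clinics in level, which the intercepts absorb. The time-by-arm term depends on slopes. When neighbouring months move together, the fitted slopes vary more than the model reports. The test then declares a changing arm effect too often, and the time-specific odds ratios it triggers get intervals that are too narrow. Whether an effect is sustained is a central question of Aim 1.

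**Working it through.** **Inputs.** The documents give no correlation, fill length, clinic size, number of clinics, prevalence or alpha, so there is no planned figure to reproduce. The number of months comes from the documents: 24 (months 13 to 36) in the body text, and at most 6 (months 13 to 18) after the cover note. Everything else below is assumed, with a two-sided 5% test.

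**Step 1: linear approximation.** Let t be the centred months, T their number, R the within-patient residual correlation matrix and M the centring matrix. The true slope variance is proportional to t'Rt/t't. The random-intercept model reports tr(MR)/(T−1) in its place. With ratio = first/second, the actual size is 2Φ(−1.96/√ratio).

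| Residual correlation (assumed) | 6 months: ratio, size | 24 months: ratio, size |
|---|---|---|
| None | 1.00, 5% | 1.00, 5% |
| AR(1), 0.5 | 1.385/0.731 = 1.89, 15% | 2.507/0.920 = 2.72, 24% |
| AR(1), 0.8 | 1.010/0.384 = 2.63, 23% | 4.651/0.724 = 6.42, 44% |
| Three-month overlapping fills (1, 2/3, 1/3, 0) | 1.705/0.689 = 2.47, 21% | 2.667/0.918 = 2.91, 25% |

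**Step 2: simulation of the logistic GLMM.** A linear approximation may misstate a logistic model, so the GLMM itself was fitted to data with no arm effect. The assumptions were 20 clinics, 30 patients per clinic, complete data, prevalence about 30%, patient and clinic intercept SDs of 1.5 and 0.4 logits, and a latent AR(1) residual. There were 300 runs per scenario.

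| Latent adjacent-month correlation | 6 months | 24 months |
|---|---|---|
| 0 | not run | 5.0% |
| 0.5 | 13.0% | 16.0% |
| 0.8 | 17.3% | 33.0% |
| 0.95 | not run | 47.0% |

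The Monte Carlo standard error is √(0.05×0.95/300) = 1.3 points at 5% and √(0.33×0.67/300) = 2.7 points at 33%. The simulated sizes are below the linear ones, and the conclusion rests on the simulated ones. In the 24-month run at 0.8, the yes/no responses had a correlation of 0.69 between adjacent months and 0.28 between the first and last. With no residual correlation the two values were 0.28 and 0.27.

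**Step 3: clinic drift.** Take a clinic trend SD of 0.1 percentage point per month, 500 patients per clinic and 30% prevalence. Ratio = 1 + 0.001²/[0.21/(500×S)], with S = t't.

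- 24 months: S = 1150, ratio 3.74, size 31%.
- 6 months: S = 17.5, ratio 1.04, size 5.5%.

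A steady drift of this size matters only over the longer follow-up.

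**Step 4: what is not affected.** The test of the time-averaged arm effect rejected 7% to 9% in all seven 300-run scenarios (the six in the table and one with clinic drift), including the one with no serial correlation. Serial correlation therefore did not drive it. An eighth scenario, with clinic drift and 150 patients per clinic, stopped at 109 runs. Its arm test rejected 37.6%, which may reflect coarse numerical integration over the clinic effect. This was not resolved, and that run is not relied on.

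**Step 5: a test that holds its size.** A t-test comparing clinic-level slopes between arms rejected 4.0% to 6.3% in the same seven scenarios.

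**The case against.** The strongest reply is that the gate no longer operates where it was written. With data ending at 18 months, 2-year and 3-year odds ratios cannot be estimated, and the cover note replaces the patient-level response for the arm comparison. The GLMM was also conditional and was to be read beside a GEE with its own adjustment for serial correlation. This stands. A reader might infer that the reported arm comparison is invalid, and the documents do not support that.

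The usual-care comparison states no time-by-arm test of its own. That it inherits one from being the same model is a fair inference, not stated text. The cover note does not say whether its model changed too.

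A reader might also extend the fault to the VIONE medication-count outcome, analysed "using generalized linear mixed models with log link". No random-effects structure or interaction test is named there, so that is missing detail and not a shown error.

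Finally, the size depends on assumed values. The Aim 1 section allows different patients each month, and the insomnia outcome is a new prescription, which may persist less than possession. Both could lower the inflation. This also stands: a flat statement that the test rejects far too often goes beyond the documents.

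None of this rescues the statement that random intercepts adjust for serial correlation over time.

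**Conclusion.** The concern holds in conditional form. The plan attributes to random intercepts an adjustment that they do not make for correlation that fades with lag, and supply-day exposure makes such correlation likely. If it is present, the time-by-arm test and the odds ratios it triggers are anti-conservative. The size is about 13% to 17% over months 13 to 18 and 16% to 33% over months 13 to 36, for assumed latent adjacent-month correlations of 0.5 to 0.8 and the simulated design above. With no residual correlation it is 5%. The 24-month figures describe the body text's plan, not the follow-up collected.

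The point reaches the usual-care comparison, to the extent that it carries the time-by-arm term, and any patient-level arm model still run. It does not reach the time-averaged arm effect to any material degree.

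**What to change.** State which GLMMs remain in use. In each of them:

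- Base inference on the arm and time-by-arm terms on clinic-clustered robust standard errors with a small-sample correction, or compare clinic-level slopes between groups.
- Optionally add a clinic random slope for time. A clinic-by-month random effect alone is not enough, because it does not cover overlapping fills within a patient.
- Say whether the usual-care model includes a time-by-arm term.

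Delete the claim that random intercepts adjust for serial correlation. For the medication-count model, name the random effects and the basis for inference.

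The cost is a change of SAP wording, longer run time and somewhat wider intervals for time-specific effects. No new data are needed.
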